- Serum hormonal markers of ovulation (P, E₂, LH, FSH)
- Presence of dominant follicle(s) on transvaginal ultrasound during and after EFV dosing
- Change in cervical mucus quality suggesting ovulation during and after EFV dosing

- c. Statistical plan including sample size justification and interim data analysis.

Sample size: We hypothesize that during co-administration of the ENG implant and reduced-dose EFV, we will detect a decrease in serum ENG concentrations, but that overall contraceptive effect will be maintained. We do not anticipate that any subjects will have a drop in ENG concentration below the threshold needed for ovulation suppression (90 pg/mL)[8]. Using a two-sided Wilcoxon test, a sample size of 15 will have 80% power (with an alpha of 0.05) to detect a 20% difference in ENG concentration between women taking EFV and historical controls. We plan to enroll 18 women to account for a potential 20% drop-out rate.

Data Analysis: We will calculate area under the curve (AUC) and maximum and minimum concentrations of each drug (C_{max} and C_{min}), as noted above. For hormone markers (LH, FSH, E₂, P) we will evaluate change over time as well as whether pertinent threshold levels are reached that could indicate that ovulation has occurred. All serum tests will be evaluated through the Johns Hopkins Division of Clinical Pharmacology, with the exception of etonogestrel concentrations as this assay is not widely available. Serum samples will be frozen and shipped to the Irving Institute for Clinical and Translational Research at Columbia University Medical Center in New York City, which will perform the etonogestrel assay.

Interpretation: If the pharmacokinetic parameters for etonogestrel that are seen in this interaction study are consistent with those published in the literature (less than 30% difference), we will conclude that there is no significant interaction between ENG and reduced-dose EFV. This would support the assertion that Nexplanon®/Implanon® is a safe and effective option for HIV-infected women taking reduced-dose EFV who desire long-acting reversible contraception. However, if two or more women out of a sample of 15 breach the threshold concentration needed for ovulation suppression, it will indicate a statistically and clinically significant decrease in ENG concentration and potential for decreased contraceptive efficacy.

Date: January 5th, 2017

Principal Investigator: [name], MPH

Application Number: NA_00087585

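### Section 7c sizes the trial to detect a 20% difference in ENG, but its 30% no-interaction rule ignores that test, so a statistically significant fall can be reported as no interaction

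*Combined protocol and SAP*

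**What the plan says.** All of the relevant text is in Section 7 (Study Statistics) of the combined protocol and SAP.

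- **Sample size (7c).** The calculation is made "Using a two-sided Wilcoxon test" and states that "a sample size of 15 will have 80% power (with an alpha of 0.05) to detect a 20% difference in ENG concentration", the comparison being "between women taking EFV and historical controls". The hypothesis is that "we will detect a decrease in serum ENG concentrations, but that overall contraceptive effect will be maintained". No woman is expected to fall below the 90 pg/mL threshold.
- **Interpretation (7c), first rule.** If the ENG parameters are "consistent with those published in the literature (less than 30% difference), we will conclude that there is no significant interaction". This is then taken as support for using the implant with reduced-dose EFV.
- **Interpretation (7c), second rule.** The trigger is put as "if two or more women out of a sample of 15 breach the threshold concentration needed for ovulation suppression". When that happens, the plan reads it as a fall in ENG that is significant both statistically and clinically, with a possible loss of contraceptive effect.
- **Primary outcome (7a).** ENG concentration before and after two weeks of EFV, which is a within-woman comparison.

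The plan gives no SD or CV, no number of historical controls and no form of the Wilcoxon test. It attaches no confidence interval or justification to the 30%, and it does not say how a significant Wilcoxon result with a difference under 30% is to be read.

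**The concern.** The effect that the trial is sized to find (20%) lies inside the zone that the Interpretation labels as no interaction (under 30%). The Wilcoxon test sets the sample size but decides none of the stated conclusions, so the 80% power does not describe the rule that does.

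The primary objective (Section 2) asks whether ENG pharmacokinetics are affected by EFV. If the hypothesis is right and a fall of about 20% is detected, the test answers yes while the first rule reports no significant interaction. That second statement is the one the plan carries forward to women with HIV who rely on the implant. The first rule also looks only at a point estimate, so an imprecise result can pass it.

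**Working it through.** **Inputs from Section 7c:** n = 15, two-sided alpha 0.05, power 80%, difference 20%, margin 30%, breach rule of at least 2 of 15. **Assumed, because the plan is silent:** the SD, a one-sample signed-rank test against a fixed reference, normal percentage differences, and one parameter.

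**1. The plan's n.** It cannot be reproduced forward without an SD. Solving backward by the normal approximation:

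SD = 20% × √15 / (1.96 + 0.84) = 27.6%.

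The t test gives 25.7%. The exact signed-rank critical value, by simulation (100,000 runs), gives about 25.0%, which is used below.

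**2. Where significance begins.** A test with 80% power at 20% becomes significant at an observed fall of about

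20% × 1.96 / 2.80 = 14%.

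To this approximation the boundary follows from the stated alpha and power alone, whatever the SD. The t-based figure is 13.9% and the log-scale figure 14.3%. Observed falls of about 14% to 30% are therefore significant and under the margin.

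**3. How often both occur** (SD 25%, n = 15, observed mean fall compared with 30%, breach clause not applied):

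| True fall | Test significant | Observed fall <30% | Significant fall and <30% |
|---|---|---|---|
| 15% | 55.5% | 99.0% | 54.6% |
| 20% | 79.9% | 94.0% | 73.9% |
| 25% | 93.7% | 78.1% | 71.8% |
| 30% | 98.7% | 50.2% | 49.0% |

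At the design effect, 73.9/79.9 = 92% of the significant results would meet the no-interaction criterion.

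**4. Sensitivity of the last column.**
- Log scale, true falls of 20%, 25% and 30%: 77%, 78% and 50%.
- Two-sample version with 15 controls and SD 18%, true falls of 20% and 25%: about 77% and 75%.
- Other SDs at a true fall of 20%: 91% for SD 20%, 55% for SD 30%, 25% for SD 40%. SDs of 30% and 40% give only about 65% and 42% power, so they contradict the plan's own claim.

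**5. Effect of the breach clause.** If each woman's chance of a breach is 1%, 5% or 10% (assumed), the chance of at least 2 of 15 is 1%, 17% or 45%. Alternatively, take the 25% SD as spread between women and assume a reference mean, since the plan gives none. The joint outcome with fewer than two breaches, at true falls of 20% and 25%, is then about:

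| Assumed reference mean | 20% fall | 25% fall |
|---|---|---|
| 300 pg/mL | 72% | 69% |
| 250 pg/mL | 67% | 61% |
| 200 pg/mL | 49% | 40% |
| 150 pg/mL | 8% | 4% |

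**6. Precision.** The 95% interval has half-width 2.145 × 25% / √15, or about 13.9 points. An observed fall of 25% has an interval of about 11% to 39%. It passes the 30% rule although falls well above 30% are not excluded.

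**The case against.** The strongest reply is that a margin of clinical relevance may properly be wider than the smallest detectable difference. Section 8a describes the goal as learning whether ENG falls to a level at which ovulation might occur, and the hypothesis itself foresees a real but tolerable decrease. If significant is read clinically, p < 0.05 with a 22% fall is no contradiction. This stands in part: 20% and 30% can coexist. But the plan does not call the 30% a clinical margin, justify it or require an interval inside it. In the breach clause it joins statistical and clinical significance without separating them.

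Second, a reader might infer that any result under 30% is called no interaction. The text does not support that, because two or more breaches signal a significant decrease whatever the mean fall. Since the plan expects no breaches, the clause does not resolve the conflict in the scenario the plan anticipates. If breaches did occur with a difference under 30%, the two rules would point opposite ways.

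Third, the rule speaks of parameters in the plural. If every one must be under 30%, the no-interaction conclusion is reached less often than a one-parameter simulation shows.

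Fourth, this is a single-arm pilot meant to guide later studies. That lowers the severity, but the Interpretation still draws a conclusion about use of the implant.

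**Conclusion.** The concern holds as a mismatch between the sizing and the first interpretation rule, and as a no-interaction rule resting on a point estimate. The conflict zone of about 14% to 30% needs only the stated alpha and power. The joint frequencies (up to about 74%, 72% and 49% at true falls of 20%, 25% and 30%) rest on the back-solved 25% SD, the arithmetic scale and one parameter. On those assumptions they are upper bounds, since breaches or a requirement on several parameters would lower them, possibly by a lot if ENG starts low.

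Three stronger readings are not supported. Test and rule do not usually disagree across the whole range from 20% to 30%, because at a true 30% fall it is about an even chance. The margin is not wrong merely for exceeding the detectable difference. And n = 15 is not shown to be wrong; without an SD it cannot be checked.

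Severity: should be fixed. The wording of the main conclusion depends on it, but design and data do not.

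**What to change.** Revise the Interpretation paragraph of 7c as follows.

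1. Report the within-woman ratio of ENG after two weeks of EFV to ENG before it (the primary outcome in 7a), with its 95% confidence interval and the pre-specified two-sided Wilcoxon test, naming the signed-rank form for paired data. Let these decide whether ENG fell during EFV. Treat the comparison with historical or literature values as supportive, since a difference there could also reflect population, time since insertion or assay.
2. If the test shows a significant fall, do not conclude that there is no significant interaction. Report a decrease, its size and whether it is under 30%.
3. State that any change is below 30% only if the whole confidence interval lies within that margin.
4. Keep the breach clause as a separate clinical statement.
5. State that the 80% power refers to detecting a 20% difference and not to the 30% rule.

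The cost is a few sentences, with no new patients, samples or visits. Some results will read less favourably, and a no-interaction conclusion becomes harder to reach. With an SD of 25% and n = 15, the observed fall would have to be below about 30 − 13.9 = 16%. The before-after spread is not given and may differ, so the precision of the ratio cannot be predicted from the plan.

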in New York City. ENG samples will be collected, frozen, and batch-shipped. The subject population will be healthy, HIV-negative women using Nexplanon®/Implanon®, with the anticipation that the findings will be applicable to HIV-infected women. There is limited data regarding the use of the etonogestrel implant in obese women. While two small studies found lower etonogestrel concentrations in obese women than normal weight women, the differences were not statistically significant[16, 17]. Overweight and obese women using the etonogestrel implant do not experience contraceptive failures more frequently than overweight or obese women using an intrauterine device[18]. We will limit enrollment to women with a BMI <30 kg/m² so as to limit any effect morbid obesity may have on etonogestrel concentrations. We expect that the study will take a total of 12 months to complete. A screening visit to confirm eligibility will occur prior to initiation of study visits.

Screening: Potential subjects will be identified by their treating providers as meeting basic eligibility criteria (appropriate age and currently using Nexplanon®/Implanon®). Each candidate will be informed of the study purpose and design, and will be given contact information for study personnel if she is interested in enrolling. With her permission, the potential subject's contact information will also be forwarded to study personnel, who will then contact her by phone. During a phone interview, details of the study will be discussed with her, after which she will be asked to come to the Bayview CRU for an in-person interview. During this visit, she will be asked to read and sign the approved consent form, undergo a history and physical exam, and have baseline laboratory tests performed (hematologic and metabolic panels as described in Inclusion Criteria, serum HIV, urine pregnancy test), as well as a baseline ultrasound to ensure her ovaries are detectable. Study personnel will review the results of the laboratory tests, and if all results are in the specified ranges, the subject will be contacted to schedule the start of the study protocol.

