Data collection: After successful screening, women will be asked to take 14 days of EFV in a once-nightly 400 mg regimen. We will collect blood samples for baseline ENG concentration on the day participants begin taking EFV, before the first dose (Day 1, times 0 hour, 1 hour, and 2 hours). The first dose of EFV will be taken in the evening of Day 1, and the next blood sample for ENG concentration will be drawn twelve to twenty hours after the first dose of EFV. (For example, if a participant takes her first dose of EFV at 10 PM on Day 1, she will be asked to return to the CRU between 10 AM and 6 PM on Day 2.) We will then obtain subsequent samples every 3 to 4 days (+/- 1 day) for the remainder of the two week EFV course and for 4 additional weeks (through Week 6 of study participation). This is a total of 14 outpatient visits, including screening. All serum samples will be analyzed for concentrations of ENG, which will be used to derive the ENG area under the concentration-time curve (AUC), the maximum and minimum observed serum drug concentration (C_{max}, C_{min}), and the apparent average serum concentration at steady-state (C_{ss,avg}) using WinNonlin®. EFV concentrations will be determined from plasma samples obtained at 2 timepoints during EFV administration, and measured using a validated LC/MS/MS assay in the Clinical Pharmacology Analytical Laboratory of the Johns Hopkins Hospital.

Table 1: Participant Visit Schedule and Timing of Study Assessments

Visit	Screening	Study Entry			Week 1		Week 2		Week 3		Week 4		Week 5		Week 6	
		1			2	7	11	14	18	21	25	28	32	35	39	42
Serum Tests		0 hr	1 hr	2 hr												
ENG		X	X	X	X	X	X	X	X	X	X	X	X	X	X	X
EFV					X			X								
FSH		X			X	X	X	X	X	X	X	X	X	X	X	X
LH		X			X	X	X	X	X	X	X	X	X	X	X	X
Estradiol		X			X	X	X	X	X	X	X	X	X	X	X	X
Progesterone		X			X	X	X	X	X	X	X	X	X	X	X	X
Safety Labs	X															X
UPT	X															X
HIV	X															X
TVUS	X				X	X	X	X	X	X	X	X	X	X	X	X
CM	X				X	X	X	X	X	X	X	X	X	X	X	X

Date: January 5th, 2017

Principal Investigator: [name], MPH

Application Number: NA_00087585

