Secondary endpoints will be serum markers of ovulation (estradiol [E₂], progesterone [P], follicle stimulating hormone [FSH], and luteinizing hormone [LH]), as well as evidence of ovulation on cervical mucus exam and transvaginal ultrasound (presence and subsequent disappearance of a dominant follicle >15 mm diameter)[19]. Blood for hormone assays will be drawn at the Bayview CRU at the same time as samples for ENG and EFV. During these visits participants will also undergo a pelvic exam for cervical mucus assessment, and a pelvic ultrasound to look for ovarian follicular activity. Monitoring throughout the study will allow us to compare ovarian activity across time points through both ultrasound visualization and ovarian hormone testing (E₂ and P). Changes in cervical mucus quality secondary to the progestin activity of ENG provide secondary contraceptive effects that may be maintained even if ovulation occurs. Continued monitoring for several weeks after cessation of EFV will allow us to follow subjects for the equivalent of a normal menstrual cycle, to ascertain whether either contraceptive effect (ovulation suppression or cervical mucus quality) was altered. Urine pregnancy tests may be repeated throughout the duration of the study as needed.

Ultrasounds and venipuncture for LH, FSH, E₂ and P levels will occur in the CRU. A total of 20 mL of venous blood will be collected for each outpatient visit. FSH, LH, E₂, and P assays will be performed by the CRU at JHU. FSH and LH will be measured using the automated immunoradiometric assay (IRMA) system. Assay sensitivity of LH assays is 0.07 mIU/ml; assay sensitivity of FSH assays is 0.2 mIU/ml. P will be measured using an automated immulite chemiluminescent assay system. Assay sensitivity of the P assay is 0.05 ng/ml. E₂ will be measured via an ultra-sensitive competitive binding radioimmunoassay with sensitivity of 2.2 pg/ml. The EFV assay will be performed through the Johns Hopkins Hospital Clinical Pharmacology Analytical Lab, and will be measured via LC-MS/MS assay with a lower limit of quantification of 0.5 ng/ml.

An assay for ENG is not commercially available, but the Irving Institute for Clinical and Translational Research at the Columbia University Medical Center in New York has developed a validated assay. ENG concentrations will be measured by LC-MS/MS, and the assay has a lower limit of quantification of 50 pg/ml.

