- Nervous system symptoms: dizziness, insomnia, impaired concentration, somnolence, abnormal dreaming, euphoria, confusion, agitation, amnesia, hallucinations, stupor, abnormal thinking, depersonalization. Mild symptoms occurred in 33.3% of patients taking EFV compared to 15.6% of patients in control groups; moderate symptoms occurred in 17.4% of patients taking EFV compared to 7.7% of controls; and severe symptoms occurred in 2% of patients taking EFV compared to 1.3% of controls.
- Rash: 26% of patients taking EFV developed a rash compared to 17% of patients in control groups. A grade 4 rash (erythema multiforme, Stevens-Johnson syndrome, toxic epidermal necrolysis, necrosis requiring surgery, exfoliative dermatitis) was seen in 0.1% of patients treated with EFV and no patients in control groups. Rashes usually occur during the first two weeks of treatment, and are mild-to-moderate maculopapular skin eruptions. The rash typically resolves within one month in patients who continue EFV.
- Hepatotoxicity: it is recommended that liver enzymes be evaluated before and during treatment with EFV, as EFV can cause elevated liver enzymes even in patients without underlying hepatic disease.
- Convulsions: Convulsions have been noted in patients treated with EFV, typically in the setting of a known seizure disorder.
- Lipid elevations: EFV can lead to increased concentrations of total cholesterol and triglycerides. Some HIV-uninfected volunteers who received EFV were noted to have 10-20% increases in total cholesterol from baseline.

Date: January 5th, 2017

Principal Investigator: [name], MPH

Application Number: NA_00087585

- **Fat redistribution:** Body fat may redistribute or accumulate in certain regions of the body, including central obesity, dorsocervical fat enlargement (buffalo hump), peripheral wasting, facial wasting, breast enlargement, and “cushingoid appearance.” This phenomenon has been noted among patients taking antiretroviral therapy in general, and while it has not been specifically linked to EFV, it is a potential adverse reaction to this drug.
- c. Justification and safety information if non-FDA approved drugs without an IND will be administered.

Not applicable

7. Study Statistics

- a. Primary outcome variable.

Primary Outcome: Serum concentrations of ENG before and after two weeks of reduced-dose EFV

- b. Secondary outcome variables.

Secondary Outcomes:

- Serum concentrations of EFV at the start and end of the study period

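### The primary outcome is ENG before and after EFV, but the only named test, its 80% power and the 30% no-interaction rule compare with unidentified historical or published values

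*Combined protocol and SAP*

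**What the plan says.** Section 7a defines the endpoint as a change over time: "Primary Outcome: Serum concentrations of ENG before and after two weeks of reduced-dose EFV". Section 4a (Data collection) supplies the baseline: "We will collect blood samples for baseline ENG concentration on the day participants begin taking EFV, before the first dose", at 0, 1 and 2 hours on Day 1. The study has a single arm.

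Section 7c (Sample size) gives a two-sided Wilcoxon test, 15 women, alpha 0.05 and 80% power "to detect a 20% difference in ENG concentration between women taking EFV and historical controls". It states no SD, no historical mean, no number of controls, and does not say whether the test is signed-rank or rank-sum.

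Section 7c (Interpretation) has two rules. The first takes ENG parameters that are "consistent with those published in the literature (less than 30% difference), we will conclude that there is no significant interaction"; the publication is not named. The second counts individual women: "However, if two or more women out of a sample of 15 breach the threshold concentration needed for ovulation suppression", with the threshold given under Sample size as 90 pg/mL. The second rule uses no historical values.

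Two other places point to a within-study comparison. The Abstract says concentrations will be compared across time points, and section 4a expects sparse sampling to be adequate for changes in ENG clearance during EFV. Neither names a test or a criterion. The Data Analysis paragraph of 7c lists AUC, Cmax and Cmin but no test of change from baseline.

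**The concern.** The outcome and the inference use different comparators. A power figure for a comparison with historical controls does not carry over to a before/after comparison, whose precision depends on the variability of the within-woman change.

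The 30% rule has the more serious problem. A ratio to published values is the product of the EFV effect and the ratio of this cohort's baseline to the published one. The protocol itself gives reasons why that second factor might not be 1:

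- Section 9a says ENG declines over the life of the implant, and sections 4a and 5 restrict entry to implants 12 to 24 months old.
- Section 4a restricts BMI "so as to limit any effect morbid obesity may have on etonogestrel concentrations".
- On the assay, section 4a says "An assay for ENG is not commercially available", so published values may come from a different one.

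Section 7c says that meeting the 30% rule would support regarding the implant as safe and effective with reduced-dose EFV. An offset in one direction would give that reassurance wrongly; an offset in the other would report an interaction that is not there. The scheduled baseline samples remove the ambiguity, but the written rule does not use them.

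**Working it through.** **1. The stated 80%.** It cannot be reproduced, because the SD, the control data and the type of Wilcoxon test are missing. Solving backwards for a 20% difference with 15 women, 80% power corresponds to:

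- a log-SD of about 0.28 (25% of the mean) against a fixed historical value;
- a log-SD of about 0.21 (18% of the mean) for a rank-sum test against 15 controls.

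A signed-rank test on 15 within-woman log ratios also gives 80% at SD 0.28. The sentence could therefore be a paired calculation with the wrong comparator written beside it; the text does not settle this.

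**2. Power for the before/after comparison.** Simulated normal log ratios, mean ln(0.80) = −0.223, n = 15, exact two-sided signed-rank test (reject if the smaller rank sum is 25 or less). The SDs are assumptions.

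| SD of log ratio | Power |
|---|---|
| 0.20 | about 97% |
| 0.28 | about 80% |
| 0.40 | about 50% |

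With between-woman log-SD s and before/after correlation ρ (one value before, one after), the SD of the log ratio is s√(2(1−ρ)). It equals 0.28 at ρ = 1 − 0.28²/(2s²), which is 0.50, 0.56 or 0.76 for s = 0.28, 0.30 or 0.40. Power exceeds 80% above that correlation and is lower below it.

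**3. Arithmetic of the 30% rule.** Let b be cohort baseline ÷ published value and c the true within-woman fall. The ratio to published is b(1 − c), and on the low side the rule is met if this exceeds 0.70. The largest fall that passes is therefore 1 − 0.70/b.

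| b | Largest fall that passes |
|---|---|
| 1.2 | 41.7% |
| 1.0 | 30% |
| 0.8 | 12.5% |
| 0.7 | 0% |

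A 40% fall passes once b exceeds 0.70/0.60 = 1.167.

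**4. Chance of passing the rule after a true 40% fall.** One geometric mean concentration, n = 15, published value taken as error-free, SE = SD/√15; P(0.70 < observed ratio < 1.30). Offsets and SDs are assumptions.

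| Baseline offset | SD 0.20 | SD 0.28 | SD 0.40 |
|---|---|---|---|
| none | 0.1% | 2% | 7% |
| +10% | 13% | 21% | 28% |
| +20% | 71% | 65% | 61% |

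Example at +20% and SD 0.28: the true ratio is 0.60 × 1.2 = 0.72 and SE = 0.28/√15 = 0.0723. Then (ln 0.70 − ln 0.72)/0.0723 = −0.39, so the chance is 65%.

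**5. The threshold rule as a backstop.** After a 40% fall a woman is below 90 pg/mL only if she started below 90/0.60 = 150 pg/mL. The chance that neither rule signals, at a +20% offset with one Day 14 sample per woman, is:

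| Assumed published mean | SD 0.20 | SD 0.28 | SD 0.40 |
|---|---|---|---|
| 150 pg/mL | 21% | 7% | 2% |
| 200 pg/mL | 71% | 60% | 37% |
| 250 pg/mL | 71% | 65% | 58% |

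These are upper-end figures, because ENG is also drawn at other visits. With three samples at the full 40% fall and an added visit-to-visit log-SD of 0.15 (assumed), 60% becomes about 35% (published 200, SD 0.28), 21% becomes about 0.5% (150, SD 0.20), and 65% becomes about 62% (250, SD 0.28).

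**6. The same 30% criterion on the within-woman ratio.** At a log-ratio SD of 0.28, a true 20% fall passes 97% of the time and a true 40% fall 1.6%. A baseline offset no longer enters.

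**The case against.** The strongest reply is that this is a slip of wording. The endpoint, the pre-dose samples, the Abstract and the remark on ENG clearance all point to a within-woman comparison. The phrase about historical controls also appears in section 2 for the EFV objective and may have been carried over. That is plausible, and it means the documents do not support inferring that the study will ignore its own baselines. But none of those places supplies a test or a criterion, so 7c still needs correcting.

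Second, the high error rates need an offset that nothing in the documents quantifies. This stands. The weight differences cited in section 4a were not statistically significant, the ENG assay is described as validated, and implant age matters only if the published cohort differs. With no offset, the rule wrongly passes a 40% fall only 0.1% to 7% of the time. A reader might infer that false reassurance is likely; the documents support only that the rule cannot exclude it, and the error could equally be a false alarm.

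Third, the model simplifies. The written rule concerns several pharmacokinetic parameters, and the calculation uses one mean concentration. This also stands, so the percentages are illustrations; the arithmetic in step 3 applies to any parameter expressed as a ratio to a published value.

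Fourth, requiring a confidence limit above 0.70 would go beyond the defect. At SD 0.28 it cuts the pass rate at a true 20% fall from 97% to 40%. Changing the comparator is enough, so the confidence-limit rule is an option only.

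**Conclusion.** The mismatch is in the text and should be fixed. As written, 80% power is not established for the stated primary outcome. A reader might infer that the study is underpowered; the documents do not support that, since paired power may be above or below 80% depending on an SD that they do not give.

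The 30% rule confounds the EFV effect with any baseline difference between cohorts and can err in both directions: a 40% fall passes at a baseline more than 16.7% above published, a fall over 12.5% fails at 20% below, and no effect at all fails at 30% below. These are exact consequences of the rule; how often they would occur depends on an offset of unknown size and direction. The threshold rule may catch most or very few missed falls, depending on a baseline level that is not stated.

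This is a should-fix point and not a barrier to the study: it is a single-arm pilot, its samples are unaffected, and the paired analysis needs no new data.

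**What to change.** Change the wording of 7c only:

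1. Name the primary analysis: the within-woman log ratio of ENG at the Day 14 visit to the mean of the three Day 1 pre-dose samples, with a two-sided Wilcoxon signed-rank test at 0.05 and the geometric mean ratio with its 95% confidence interval. Use concentration, because pre-dose sampling spans only 2 hours and gives no matching baseline AUC.
2. Apply the existing 30% criterion to that ratio instead of to published values. Report the interval and the signed-rank result beside it, so that a smaller significant fall is not described as no interaction. At SD 0.28 and a true 20% fall, the two results coincide in at least about 76% of trials (0.968 + 0.797 − 1 = 0.765). The sponsor may choose the stricter rule of a lower confidence limit above 0.70, but the fix does not require it.
3. Name the published source and keep that comparison descriptive.
4. Restate the power sentence for the paired test with a stated and sourced SD of the log ratio, for example: 15 completers give about 97%, 80% or 50% power for a 20% fall at SD 0.20, 0.28 or 0.40. The 0.28 is only the value at which 80% holds, not an estimate.
5. Leave the threshold rule unchanged.

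Cost: no new samples, visits or participants. The sponsor must justify a within-woman SD, and the stated power may then differ from 80%.
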